6.1.3 Concomitant therapy

There are no restrictions on use of concomitant medications. However, for those who are randomized to nipple stimulation, the use of exogenous oxytocin intravenous solution will not be permitted until at least two hours of nipple stimulation alone has been attempted, unless this is decided by the treating obstetric provider. Stimulation may be discontinued at any time that the treating obstetric provider decides. If there are any signs of fetal heart rate abnormalities on the cardiotocography, the obstetric provider should provide usual care measures such as discontinuation of stimulation, lateral positioning, intravenous hydration, etc. Initiation of exogenous oxytocin intravenous solution prior to two hours of nipple stimulation alone will be considered a cross-over.

6.2 Assessments

Obstetric and perinatal clinical outcomes will be assessed and abstracted through chart review of the electronic medical record of both subjects and their infants by certified trained research members according to the outcome definitions listed in the protocol. Postpartum assessments will be conducted at 2 weeks postpartum and 4-12 weeks postpartum. While the ideal time period is 6-8 weeks postpartum, such a short time-window for follow-up may result in less-than-ideal protocol adherence, and 12 weeks is still within the typically described postpartum period (the “4th trimester”). In addition, economic costs and infant feeding method will be assessed at 6 months postpartum.

To assess patient-centered outcomes, several study questionnaires will be conducted:

1. To assess subject-reported pain experienced during childbirth, the visual analog pain scale (28) will be administered at three different timepoints: (1) prior to initiating study intervention (to obtain baseline); (2) two hours after initiating study intervention; and (3) during postpartum stay prior to delivery hospitalization discharge.
2. To assess subject-reported satisfaction with the childbirth process, the Birth Satisfaction Scale-Revised (BSS-R) (30) (31) will be administered during postpartum stay prior to delivery hospitalization discharge.
3. To assess subject-reported feelings of control during childbirth, the Labor Agency questionnaire (29) will be administered during postpartum stay prior to delivery hospitalization discharge.

4. To assess subject-reported feelings of depression after childbirth, the Edinburgh Postnatal Depression Scale (EPDS) (32) will be administered at two different timepoints: (1) prior to initiating study intervention (to obtain baseline) and (2) at 4-12 weeks postpartum (ideally 6-8 weeks postpartum). The baseline EPDS will be reviewed, and the total score will be tabulated in real-time. The EPDS at 4-12 weeks postpartum will be completed by the subject online or with a certified study team member via telephone. A certified study team member will check daily (Monday-Friday) to review any completed online surveys and tabulate scores during these daily (Monday-Friday) reviews. If the EPDS at 4-12 weeks postpartum is completed with the subject via telephone, the total score will be tabulated at the conclusion of the telephone encounter. Any score ≥ 10 on either the baseline or 4-12 weeks postpartum EPDS will be reported to the subject's primary obstetric provider team as this is the threshold that suggests increased risk of depressive illness.
5. Prior to delivery hospitalization discharge, subjects will be asked if they had any intrapartum expression of colostrum or breast milk, the quantity (mL or ounces) expressed if known, whether they collected and stored it for their infant, and whether they fed it to their infant.
6. After delivery hospitalization discharge 2 weeks postpartum, all subjects will be administered the Perception of Inadequate Milk Supply (PIMS) (40) survey to assess their perception of their milk supply. In addition, the EQ-5D[™] and EQ-TIPS[™] surveys will be administered.
7. After delivery hospitalization discharge, between 4 to 12 weeks postpartum (ideally 6 to 8 weeks postpartum), all subjects will be contacted by text message, telephone, or by email (based on subject preference) to evaluate if they experienced any unanticipated outpatient or inpatient visits for them or their infants since delivery hospitalization discharge. Subjects will also be asked if they ever attempted to breastfeed postnatally.
8. Among subjects who state they attempted to breastfeed at least once postnatally; these subjects will be administered the Maternal Breastfeeding Evaluation Scale (MBES) (33) between 4 to 12 weeks postpartum (ideally 6 to 8 weeks postpartum) to assess their breastfeeding success. In addition, the EQ-5D[™] and EQ-TIPS[™] surveys will be administered.
9. After delivery hospitalization discharge, at 6 months postpartum, all subjects will be sent an electronic survey to assess infant feeding method. In addition, the EQ-5D[™] and EQ-TIPS[™] surveys will be administered. Subjects may be contacted by telephone or by email (based on subject preference) to follow-up any incomplete surveys.
10. For spontaneous labor control patients, time/duration since contractions began, receipt of outpatient prostaglandins such as misoprostol, outpatient nipple stimulation, and time of

last membrane stripping will be collected by a combination of patient recall and medical record review.

11. Oxytocin concentration will be measured by mass spectrometry. Cytokines will be determined by enzyme-linked immunosorbent assay.

12. Plasma samples will be analyzed for proteomic profile by the Keck MS & Proteomic Resource and for microRNAs by the Yale Center for Genome Analysis. De-identified urine samples will be sent to an external core facility with expertise in prostaglandin measurement (Vanderbilt Eicosanoid Laboratory).

13. Milk samples will be analyzed at the [name] Lab (Cornell University, Ithaca). Sodium concentration and conductivity in milk will be measured using the LAQUATwin electrodes (Horiba, TX, USA). Milk lactose, fat and total protein will be measured in samples where a larger milk volume (>1ml) is available using the SpectraStar™ XT-R - High-Performance Extended Range NIR Analyzer (KPM, Analytics, MA, USA).

6.2.1 Efficacy

6.2.2 Safety/Pregnancy-related policy

The study protocol has been designed to minimize risks to subjects and their neonates including the requirement for continuous fetal monitoring during receipt of either study intervention, as well as detailed steps outlined to ensure the desired contraction frequency pattern to minimize risk of abnormal fetal heart rate patterns. All subjects who are undergoing continuous fetal monitoring are observed by labor nurses, and fetal monitoring is continuously reviewed and recorded.

6.2.2.1 Adverse Events Definition and Reporting

Adverse study events are expected to be rare. However, Reportable Events (which are events that are serious or life-threatening and unanticipated (or anticipated but occurring with a greater frequency than expected) and possibly, probably, or definitely related to study procedures or Unanticipated Problems Involving Risks to Subjects or Others (UPIRSO) that may require a temporary or permanent interruption of study activities, as determined by the Principal Investigator or sub-site PI(s) will be reported to the Yale IRB. Events that may require a temporary or permanent interruption of study activities by the Principal Investigator to avoid potential harm to subjects will be reported to the IRB **immediately** (if possible), followed by a written report to the IRB using the UPIRSO Reporting Form (710 FR 4) **no more than 5 calendar days** after the Yale Principal Investigator ([name]) becomes aware of the event.

Detailed information concerning adverse events will be collected and evaluated throughout the conduct of the protocol. Any adverse events deemed serious unexpected and definitely, possibly or probably related, will be immediately (within twenty-four hours of notification)

forwarded by the Yale Principal Investigator ([name]) to the DSMC Chair and any other DSMC member who requests notification. If a death is reported, a copy of the patient's medical record will be made.

Adverse events which do not qualify under the below definition will be collected and sent to the Chair, and any other requesting DSMC member on a monthly basis. The Chair decides whether the adverse event reports should be disseminated to the rest of the committee, and whether a follow-up call or meeting is required. All adverse events will be considered along with other interim safety data in the DSMC deliberations.

The following events may represent UPIRSOs that should be promptly reported:

- Adverse device effects that are unanticipated
- Adverse events or injuries that are serious, unexpected, *and* related
- Breaches of confidentiality involving risks
- Revisions to safety information, such as Investigational New Drug (IND) Safety Reports and MedWatch Reports, that meet the definition of a UPIRSO
- New information indicating an unexpected increase in risks or decrease in potential benefits (e.g., literature/scientific reports or other published findings)
- Protocol deviations, violations, or other accidental or unintentional changes to the protocol or procedures involving risks or with the potential to recur
- Unapproved changes made to the research to eliminate an apparent immediate hazard to a subject
- Other problem or finding (e.g., loss of study data or forms) that an investigator or research staff member believes could influence the safe conduct of the research

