7.4 Deviations/Unanticipated Problems

If the study team becomes aware of an anticipated problem (e.g., data breach, protocol deviation), the event will be reported to the IRB office within five (5) working days of becoming aware of the incident/issue via a Reportable New Information (RNI) mechanism in IRES IRB.

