We will establish an independent study-specific Data Safety and Monitoring Board (DSMB) to oversee the trial. Members of the DSMB will be at least four physicians who represent the appropriate expertise (perinatology, epidemiology, biostatistics, neonatology, and clinical trials) and will provide appropriate oversight to assure that the trial accrues at a sufficient rate, and that the safety and privacy of all study participants is assured. Members will not be involved in any aspect of the trial operation. The DSMB will meet regularly (at least quarterly) to review study progress and to monitor adverse events. The DSMB will be briefed before each meeting regarding study progress (recruitments and drop-outs), and study outcomes. The DSMB will issue a written report to the investigators after each meeting outlining any study problems or needed actions

3. Adverse event reporting: Detailed information concerning adverse events will be collected and evaluated throughout the conduct of the protocol (Appendix). The PI and DSMB will determine whether the adverse event meets the criteria for a Serious Adverse Event (SAE). If a participant develops a serious adverse event, the safety of continuing the intervention will be ascertained by the subject's obstetric care provider in collaboration with the PI. The Principal Investigator will conduct a review of all adverse events upon completion of every study subject. The DSMB will review all Adverse Event Reports and other interim safety data and will provide a report to the local IRB in compliance with local standards. The PI and the DSMB will evaluate the frequency and severity of the adverse events and determine if modifications to the protocol or consent form are required.

4. Attribution of Adverse Events:

Adverse events will be monitored for each subject participating in the study and attributed to the study procedures/design by the Principal Investigator and the DSMB according to the following categories:

- a.) Definite: Adverse event is clearly related to investigational procedures(s)/agent(s).
- b.) Probable: Adverse event is likely related to investigational procedures(s)/agent(s).
- c.) Possible: Adverse event may be related to investigational procedures(s)/agent(s).
- d.) Unlikely: Adverse event is likely not to be related to the investigational procedures(s)/agent(s).
- e.) Unrelated: Adverse event is clearly not related to investigational procedures(s)/agent(s).

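### Twenty-four-hour notice to the safety board depends on attribution, so a death or severe neonatal injury classed as unlikely or not related waits for the monthly batch

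*Protocol*

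**What the plan says.** Protocol section 6.2.2.1 sets up two routes to the safety board.

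- **Expedited.** "Any adverse events deemed serious unexpected and definitely, possibly or probably related, will be immediately (within twenty-four hours of notification" sent by the Yale Principal Investigator "to the DSMC Chair and any other DSMC member who requests notification". All three conditions must hold: serious, unexpected, and at least possibly related.
- **Monthly.** "Adverse events which do not qualify under the below definition will be collected and sent to the Chair", and the same sentence continues to the other recipients: "sent to the Chair, and any other requesting DSMC member on a monthly basis". The Chair then decides on wider circulation and on any follow-up call or meeting.

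For a death, the section adds only that the medical record is copied. It also says that the committee's deliberations take in all adverse events.

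Section 7.12 provides a five-level causality scale that ends in *Unlikely* and *Unrelated*, and gives attribution to the Principal Investigator and the board together. Seriousness is also shared: "The PI and DSMB will determine whether the adverse event meets the criteria for a Serious Adverse Event (SAE". On frequency: "The DSMB will meet regularly (at least quarterly". The board reviews all adverse event reports and is briefed on study outcomes before each meeting. Section 5.1 states that blinding of investigators is not feasible.

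**The concern.** Attribution of a single case is a weak gate here. Section 7.12 itself says that data on nipple stimulation are limited, and those who see the event first know the arm. For rare, severe intrapartum and neonatal events, one case can seldom be attributed with confidence. What the board needs is early sight of each such event, by arm. Section 6.4.3.5 plans no interim analysis, so adverse event reports and outcome briefings are the main independent check while the trial runs.

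The order of steps is also unclear. Prompt notice to the board depends on judgements that section 7.12 assigns partly to the board.

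**Working it through.** No figure in the plan bears on this rule, so the check is to trace one event through the text and then size the delay and the remedy.

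**Tracing a neonatal death classed *Unlikely***

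1. Section 7.11: site investigators are told of any adverse event on discovery, so the information exists at once.
2. Section 7.12: *Unlikely* lies outside definite, probable and possible.
3. Section 6.2.2.1: the relatedness condition fails, so there is no 24-hour notice. The sentence on deaths gives no time limit and no recipient, so it does not override this.
4. Section 6.2.2.1: the event joins the monthly batch, to the Chair and any requesting member.
5. Sections 6.2.2.1 and 7.12: the full board considers it at its next meeting, or sooner if the Chair circulates it or calls a meeting.
6. Section 7.12, item 5: prompt reporting to the IRB also requires at least a possible relation, so that route does not fill the gap.

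A serious, related but expected event takes the same monthly route.

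**Comparing the two routes**

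| | Expedited | Monthly |
|---|---|---|
| Condition | serious, unexpected, at least possibly related | all other events |
| Recipients | Chair and requesting members | Chair and requesting members |
| Time | 24 hours from notification | up to about a month |
| Full board | next meeting, or sooner | next meeting, or sooner |

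Only the third row differs in effect: about a month at most instead of one day, to the same people. It would be wrong to add a month to a quarter and set the total against 24 hours, because the expedited route does not go automatically to the full board either.

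**Who decides first**

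Section 6.2.2.1 uses a passive verb and names no judge. Section 7.12 names the Principal Investigator and the board jointly. A board that meets at least quarterly cannot ordinarily give its view before a 24-hour notice, so the first call most plausibly rests with the investigator. That is an inference; no section states it.

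**Sizes**

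- Women randomised per monthly cycle: 988 over the 57 months from October 2021 to June 2026 gives 988 / 57 = 17.3 on average. Sites opened at different times, so actual accrual is uneven.
- Extra expedited reports under the fix: assume that 0.5 to 2% of women have a listed event. Then 0.005 × 988 = 4.9 and 0.02 × 988 = 19.8, or about 5 to 20 over the whole trial. This is an upper bound for that range, because some of these events would already meet the expedited criterion.

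**The case against.** The strongest reply is that limiting expedited notice to serious, unexpected and related events is a legitimate design choice, and that the board loses no information. That is right as far as it goes. A reader might infer several stronger criticisms that the protocol does not support:

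- **That monthly events go to the Chair alone.** They do not. Both routes also reach any member who asks.
- **That events are hidden from the board.** Section 6.2.2.1 has all adverse events considered in deliberations, and section 7.12 has the board review all reports and receive outcome briefings. Deaths, maternal ICU admission and severe neonatal morbidity are outcomes under section 5.2.2.
- **That the investigator alone decides.** Section 7.12 shares attribution and seriousness with the board. Only the order of events suggests that the investigator judges first.
- **That the monthly route refers to a definition that is not there.** The list that follows includes serious, unexpected and related events, so the criterion is restated. The cross-reference is loose because that list also covers non-medical problems.
- **That the IRB deadlines flatly conflict.** Section 6.2.2.1 gives "no more than 5 calendar days" for the written report on events that may interrupt the study. Section 7.4 says of breaches and deviations that "the event will be reported to the IRB office within five (5) working days of becoming aware". They overlap only for a deviation serious enough to interrupt the study.

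Three further replies have force. A possible relation is enough to trigger notice. Section 7.12 expects no serious or life-threatening events, so the unexpectedness condition may exclude few. And an excess in one arm is seen in accumulated data, which the board already receives at least quarterly. The adverse event appendix that section 7.12 cites is not in the text at hand and may say more. None of this supplies a 24-hour notice for a death classed *Unlikely* or *Unrelated*.

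**Conclusion.** The point holds as a weakness of timing. A death or severe neonatal injury judged unlikely or not related has no stated 24-hour notice and may reach the Chair and requesting members up to about a month later. Full-board review then follows at the next meeting, at least quarterly. The protocol also leaves unclear who makes the classification that starts the 24-hour clock, since it shares that judgement with the body waiting to be notified.

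This is a worthwhile, low-cost improvement to the safety plan; it does not show that the plan fails. The month is read from the stated reporting cycle, and the first call by an unblinded investigator is inferred. How many events would be affected cannot be known from the protocol, which gives no expected rates for them.

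**What to change.** In section 6.2.2.1, add a short fixed list of events that go to the DSMB Chair and requesting members within 24 hours of notification, whatever the attribution or expectedness: maternal death, intrapartum fetal or neonatal death, maternal ICU admission, and neonatal encephalopathy, seizures or hypothermic treatment. All are already collected as outcomes or components of the neonatal composite. Keep the present rule for everything else.

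In section 7.12, state that the site PI makes the initial classification of seriousness and causality and that the DSMB may reclassify.

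As minor tidying, point the monthly rule at the exact expedited criterion, use one name for the safety board (DSMC in one section, DSMB in the other), and reconcile the calendar-day and working-day IRB deadlines where they overlap.

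The cost is a wording amendment and a small number of extra expedited reports. No treatment, endpoint, sample size or data item changes.

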6.2.3 Pharmacokinetics (if applicable)

Oxytocin concentration will be measured by enzyme-linked immunosorbent assay (ELISA) using a commercially available kit using internal standards and controls to assess intra-assay and inter-assay coefficients of variance. All samples will be run in duplicate. The primary outcome is the difference (delta) in oxytocin concentration between baseline and when the patient first achieves adequate contraction pattern in patients undergoing nipple stimulation compared to patients receiving exogenous oxytocin.

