4.1 Hypothesis

Our central hypothesis is that nipple stimulation with an electronic breast pump to induce labor increases spontaneous vaginal delivery, shortens duration of labor induction, improves patient-reported pain scores during labor, improves patient satisfaction and sense of self agency with the birthing process, and improve scores on the postpartum depression scale. We also hypothesize that participants assigned to nipple stimulation therapy during labor will be more likely to use breastfeeding as the sole source of nutrition at hospital discharge, which will be associated with improved maternal perception of milk supply, less severe newborn weight loss, and sustained breastfeeding for the recommended 6 months. Secondly, we hypothesize that intrapartum nipple stimulation will not increase fetal or neonatal morbidity outcomes. Last, by examining cost of care and health-related quality of life, we hypothesize that performing nipple stimulation therapy during labor will be more cost-effective than the comparator after considering their overall impact on labor and delivery, breastfeeding, and early infant nutrition and care in the first 6 months.

We also hypothesize that nipple stimulation therapy invokes the wide cascade of events that promote labor to a greater extent than IV oxytocin alone. We hypothesize that oxytocin in the plasma of patients performing nipple stimulation will rise less than among subjects receiving IV oxytocin at the time when the subject is first contracting regularly. We hypothesize that other proteins associated with labor (including but not limited to IL6, IL1beta, plasminogen activator inhibitor 1, C reactive protein, ICOS ligand, and ERP29 will rise more in the circulation of subjects receiving nipple stimulation therapy compared with IV oxytocin. We hypothesize that urinary metabolites of prostaglandin E2 and F2alpha will be higher in subjects receiving nipple stimulation therapy. We hypothesize that, on a systematic level, plasma changes among subjects partaking in nipple stimulation will differ from subjects receiving IV oxytocin. We hypothesize that nipple stimulation therapy will have earlier secretory activation as measured by milk sodium and conductivity) in the early days postpartum, compared to individuals receiving IV oxytocin alone.

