Specimen collection will be conducted as described in the previously published methodology (38).

For patients in non-spontaneous labor, blood and urine will be collected at 1) prior to cervical ripening, 2) after cervical ripening, and 3) after 2 hours of treatment (IV oxytocin or nipple stimulation). This is a maximum of 3 blood samples per subject. For control patients in spontaneous labor, a blood and urine specimen will be obtained at enrollment. Blood may be drawn in several ways depending on what is clinically appropriate: (1) venipuncture; (2) IV catheter placed as part of standard of care (SOC); and/or (3) IV catheter placed for research purposes. The research IV may be placed in addition to the SOC IV and may be used instead of research venipuncture. That is, research venipuncture and research IV will not both occur at the same time (only one or the other).

Urine samples (amount variable by patient) will be collected mid-stream in a sterile screw-top container 1) prior to cervical ripening, 2) after cervical ripening, and 3) after 2 hours of treatment (IV oxytocin or nipple stimulation). If a patient has an indwelling foley catheter, urine from the tubing will be collected at the time of adequate contractions. If a patient is being intermittently catheterized for urine, a urine sample will be collected as able, but the patient will not undergo additional bladder catheterization for the purpose of this study.

Blood and urine samples may not be collected at one or more of the specified time points due to logistical issues (eg. patient enrolled after cervical ripening, labor floor acuity prevents nurse from drawing blood, patient delivers before time point, etc.) and/or clinical care taking precedence.

Proteomic profiling will be conducted by mass spectrometry at the Keck MS & Proteomics Resource. Prostaglandin measurements will be performed by an external core facility with expertise in prostaglandin mass spectrometry methods (Vanderbilt Eicosanoid Facility). microRNA profiling will be conducted via bulk RNA sequencing by the Yale Center for Genome Analysis/Keck Core.

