2) The sample size of 988 for the primary outcome will be sufficient to detect a 9.4% or 10.8% absolute difference in breastfeeding as the sole source of nutrition (BSSN) at the time of delivery hospitalization postpartum discharge with 80% power and 90% power, respectively (two-sided test, $\alpha=0.05$). This represents the difference between an expected BSSN rate of 47% in the setting of synthetic oxytocin infusion without nipple stimulation (average rate at the study sites based on institutional data) and 56.4% (with 80% power) or 57.8% (with 90% power) with nipple stimulation therapy.

3) Assuming a 15% attrition rate at 2 weeks postpartum (the time frame for our primary cost-effectiveness analysis in Aim 3), the sample size of 988 will have 90% power for detecting a standardized effect size of 0.22 for the between-group difference in cost and difference in quality adjusted life years (QALY) (two-sided test, $\alpha=0.05$). This is considered a small effect size based on conventional criteria, hence if we observe an even larger effect size, we should be sufficiently powered.

The sample size for this biospecimen trial is based on the primary comparison, specifically the difference in primary biomarkers from baseline to after 2 hours of treatment between patients performing nipple stimulation therapy and those receiving IV oxytocin. Sample size calculations are based on differences between non-laboring and laboring patients from prior reports (Table). Sample size was determined to achieve 80% power to detect a difference with a two-tailed alpha level of 0.05. The final sample size of 48 per exposure group is based on the largest sample size required (IL1beta). Therefore, there is more than adequate power for the remainder of the biomarkers of interest.

To detect a 10 mM difference in sodium concentration between the intrapartum nipple stimulation therapy group and the immediate synthetic oxytocin infusion group at 48 hours postpartum, with a standard deviation of 20 mM, 80% power, and a significance level of 0.05, a sample size of 32 participants per group is required. Accounting for an expected 30% dropout rate, we plan to recruit 46 participants per group.

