^a Sample size (per group) that would provide 80% power to detect the reported group difference with the reported standard deviation using two-tailed tests. ^b For percent change in oxytocin, effect size was estimated based on average values in two treatment groups at the time of adequate contractions in our preliminary data. For MS data, effect size was estimated based on group differences expressed in log scale ratios converted to typical laboratory units. n/a indicates concentration in maternal circulation is unknown for estimation. Effect size refers to effect size if the study was only powered for that biomarker. ^c Detectable difference is calculated as what difference we anticipate being able to identify given the final sample size of 48. For MS counts,					

^d Based on our preliminary data

^e MS counts

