The primary comparison for Aim 1 is the difference in biomarker concentration or MS counts from baseline to 2 hours of treatment between patients performing nipple stimulation therapy and those receiving IV oxytocin. Secondary comparisons evaluate the change with labor induction versus spontaneous labor. This unadjusted between-group comparison of the within-group change will be based on a Student's t-test, with a supportive analysis using Analysis of Covariance (ANCOVA) where the baseline biomarker level will be a covariate in a mean response profile model (MRP), which allows for different variances and covariances across time. The primary exposure variable will be treatment group with either compound symmetry (CS) covariance or heterogenous compound symmetry covariance (HCS) to account for the within-patient correlation in biomarker values across the time points of data collection; and the choice between the two covariance matrices will be made using a likelihood ratio test (LRT)

as these are nested models. Results will be summarized as estimated means of fold change at adequate contractions for each group and the between-group mean differences, with surrounding 95% Confidence Intervals. By specifying the model as an MRP, we can also conduct any comparisons of means (within/between groups across time), by using linear contrasts and the multivariate Wald Test. In the adjusted analyses, we will include in the MRP as covariates the between-group differences identified in the between-group comparisons. In a sensitivity analysis, since we will know the timing of each measurement relative to the initiation of treatment, we will use the actual time (compare linear, polynomial or spline effect of time) instead of the categorical time point in a linear mixed effects model (LME) with a random intercept for each woman and a possible random slope for each woman (also tested using an LRT). All biomarkers listed in the Table will be analyzed in the same manner, as all will be treated as continuous variables. For the exploratory hypothesis using the time to active labor, we will use a joint modeling approach: time to active labor modeled jointly with the mean trajectory of change over time in biomarker values; this model will allow us to estimate the between-group differences in the time to active labor, as it is also influenced by the biomarker values within each group.

Data Analysis Plan for the Milk Biospecimen Sub-Study:

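### The Yale sub-study's oxytocin primary outcome is set at first adequate contractions, where no blood draw is scheduled, while the sizing and analysis sections set it at 2 hours

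*Protocol*

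**What the plan says.** Protocol 6.2.3 defines the oxytocin endpoint: "The primary outcome is the difference (delta) in oxytocin concentration between baseline and when the patient first achieves adequate contraction pattern". The hypothesis in 4.1 uses much the same moment, expecting a smaller oxytocin rise with nipple stimulation "at the time when the subject is first contracting regularly". Section 5.2.2 lists changes in plasma proteins and microRNA that run to adequate contractions as well as to 2 hours.

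The blood schedule in 6.3 (Biospecimen Procedures) has three draws for induced patients: before cervical ripening, after ripening, and after 2 hours of treatment. It adds "This is a maximum of 3 blood samples per subject".

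Section 6.4.2 sizes the sub-study on "the difference in primary biomarkers from baseline to after 2 hours of treatment". Section 6.4.3.2 repeats the 2-hour comparison as primary, then says in the same paragraph: "Results will be summarized as estimated means of fold change at adequate contractions for each group".

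For spontaneous-labour controls, 6.3 says: "For control patients in spontaneous labor, a blood and urine specimen will be obtained at enrollment". The Synopsis and 6.4.3.2 nevertheless plan to evaluate change in that cohort.

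On the assay, 6.2 says "Oxytocin concentration will be measured by mass spectrometry", while 6.2.3 says ELISA.

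**The concern.** The sample-size table in 6.4.2 marks oxytocin as a primary biomarker. Followed literally, 6.2.3 asks for a measurement that the schedule does not provide, and blood not drawn in labour cannot be recovered later. An analysis plan written afterwards could not repair that.

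The two time points also answer different questions. In the control arm, 6.3 allows the infusion rate to be raised every 15 minutes over the first 2 hours, and 2.1 describes concentrations that rise with dose. A 2-hour sample compares the arms at a fixed time, during or just after titration. A sample at adequate contractions compares them at the same uterine response. The pilot argument in 2.1, that nipple stimulation reached the same contraction pattern with a smaller oxytocin change, concerns the second question.

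**Working it through.** **1. Time points side by side.**
- First adequate or regular contractions: 4.1 (oxytocin hypothesis), 5.2.2 (plasma change outcomes), 6.2.3 (oxytocin primary outcome), 6.4.3.2 (results summary).
- 2 hours of treatment: 5.2.2 (plasma profiles), 6.4.2 (basis of the sample size), 6.4.3.2 (primary comparison).

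Section 6.4.3.2 therefore disagrees with itself.

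**2. Scheduled samples.** There are three blood draws, and none is tied to adequate contractions. The only specimen that 6.3 ties to that moment is urine from an indwelling catheter. A patient with all three draws has reached the cap, so an additional draw would break it.

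**3. Baseline.** Section 5.2.2 explains baseline only as before treatment. The pre-ripening and post-ripening samples both precede treatment. Section 6.3 accepts that some patients enroll after ripening and so lack the first sample.

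**4. Assay.** Section 6.2 gives mass spectrometry for oxytocin and ELISA for cytokines; 6.2.3 gives ELISA for oxytocin.

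**5. Controls.** A change needs two samples, and 6.3 schedules one. Section 6.3.7 says that controls with labour complications will not be sampled on entering active labour, which implies a second collection that 6.3 does not list. Even if taken, it would give a change from early to active labour, not from pre-treatment to 2 hours.

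**6. Oxytocin sizing.** Inputs from the 6.4.2 table: difference 24.25%, SD 40.8, two-sided alpha 0.05, power 80%.
- n per group = 2 × SD² × (1.960 + 0.842)² / difference² = 2 × 40.8² × 2.802² / 24.25² = 44.4, rounded up to 45. The table states 45.
- Standard error of the difference at 48 per group = 40.8 × √(2/48) = 8.33.
- Power at 48 = Φ(24.25/8.33 − 1.960) = Φ(0.95), about 83%. A t-test calculation gives 82%.
- Detectable difference at 48 = 2.802 × 8.33 = 23.3%. The t-test gives 23.6%, the stated figure.

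The arithmetic is sound; the open question is the time point. For oxytocin, footnote b says "effect size was estimated based on average values in two treatment groups at the time of adequate contractions in our preliminary data". The documents give no 2-hour effect. As an assumption, keep the SD at 40.8 and let the 2-hour difference be a fraction of 24.25 (normal approximation):

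| Fraction | Difference | Power at 48 per group | n per group for 80% power |
|---|---|---|---|
| 100% | 24.25 | 83% | 45 |
| 90% | 21.83 | 75% | 55 |
| 75% | 18.19 | 59% | 79 |
| 50% | 12.13 | 31% | 178 |

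A larger 2-hour difference would raise power. The documents do not say which way it goes.

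**The case against.** The strongest reply is that the sample-size text, the stated primary comparison and the blood schedule all agree on 2 hours, so the primary biomarker comparison can be run as scheduled and 6.2.3 is simply out of line. That stands, and it limits the severity. It does not remove the problem: 6.2.3 still names a different primary outcome, the hypothesis supports it, and 6.4.3.2 uses both times.

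Four stronger readings are tempting, and the documents do not support them.

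- A reader might multiply two times, two baselines and two assays into many selectable versions of the outcome. But a time with no blood sample cannot be chosen afterwards, and an assay can be chosen only if both are run.
- A reader might say that no control can have a change value. That is true of the 6.3 schedule, but 6.3.7 implies a second sample, so the passages conflict rather than settle the matter. Comparing controls on level, as 5.2.2 plans, remains possible.
- A reader might say that a pre-ripening baseline biases the treatment effect. The primary comparison is between randomised arms, and ripening precedes the assigned treatment, so the main effect is added noise. The pre-treatment gloss in 5.2.2 makes the post-ripening sample the natural reading, though not an explicit one.
- A reader might say that the 24.25% was measured at adequate contractions. Footnote b dates the effect-size column (528 pg/mL). The 24.25% carries footnote d, which cites preliminary data without a time. Oxytocin also does not set the sub-study size: 6.4.2 bases the 48 per group on IL-1beta.

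**Conclusion.** The contradiction is real and should be fixed. The oxytocin primary outcome in 6.2.3 has no scheduled blood sample at its second time point, and the protocol elsewhere names a different primary time. The unfixed baseline, the two assays and the mismatch over control sampling leave the outcome further under-defined.

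The oxytocin power of about 82% at 48 per group follows from the table, but it is not shown to hold at 2 hours. The lower powers in the table above are illustrations under an assumed constant SD, not evidence that the sub-study is underpowered.

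The point is confined to the Yale biospecimen sub-study. Spontaneous vaginal delivery, the trial's primary outcome, is unaffected.

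**What to change.** 1. State one primary biomarker outcome throughout: the change from the post-ripening, pre-treatment sample to the 2-hour sample, measured with one named assay. Amend 4.1, 5.2.2, 6.2, 6.2.3 and 6.4.3.2 to match, and remove adequate contractions as a time point for plasma.
2. Reconcile the Synopsis, 6.3, 6.3.7 and 6.4.3.2 on control sampling. If only the enrollment sample is taken, compare controls on level only, as 5.2.2 already does.
3. Note in 6.4.2 that the oxytocin effect-size column comes from adequate contractions and that no 2-hour effect is available.
4. Optionally, make the baseline-adjusted ANCOVA already planned in 6.4.3.2 the primary test. With equal variances and correlation r between the two samples, its variance relative to the change score is (1 − r²)/(2(1 − r)) = (1 + r)/2, or 0.75 at an assumed r of 0.5. This is a gain in precision, not a correction.

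Items 1 to 3 are wording changes and add no blood draw. The cost is scientific: the comparison of plasma oxytocin at the same contraction pattern, which motivated the hypothesis, is given up. If the investigators want to keep it, the schedule must change instead, by raising the three-draw cap or giving up an existing draw.
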